### **Health Preference by HT Complication Status**

The SF-6D preference will be calculated by the HK population specific

algorithm^15 by HT complication status. Independent t-test will be used to compare the SF-6D values of HT patients with each complication to those without any complication, and between RAMP-HT and usual care HT patients.

All above statistical analyses will be performed using STATA Version 13.0 (StataCorp LP. College Station, Texas, U.S.). All significance tests will be two-tailed and those with a p-value less than 0.05 will be considered statistically significant.

#### **Cost Effectiveness Analysis of RAMP-HT by Markov Modeling**

To evaluate the long term cost-effectiveness of RAMP-HT, a Markov model will be developed based on the natural history of a patient population, with similar distribution of age and gender as the RAMP-HT cohort, to simulate disease development over a lifetime. The structure of the model will be established as shown in Figure 1. At the end of each year, each HT subject may die, develop one HT complication or stay alive without complications. For subjects who develop complications, they may die immediately from the complication, die from other cause of death or stay alive in the complication health state.

The transition probabilities of developing complications and death from year to year will be estimated from the observed complication rates from the 5-year cohort study for RAMP-HT and usual care HT patients as described above. HT complication related mortality rates will be estimated by a review of published and unpublished local and overseas literature. Hong Kong standard life table will be used as a benchmark of survival presenting HT related mortality and mortality from other causes in Hong Kong local population among different demographic groups (e.g. age and sex). The cumulated life-years of the RAMP-HT and usual care cohorts will be calculated. The average cost and preference values for each HT disease state (with or without specific complication) obtained from the cost and

preference studies described above will be applied to the model to determine the cumulative quality adjusted life years (QALY) and lifetime costs for RAMP-HT and usual care cohorts.

The measure of cost-effectiveness of RAMP-HT will be the incremental cost-effectiveness ratio (ICER) in term of cost per QALY gained by RAMP-HT group compared to usual care. By comparing the between-group-differences in average lifetime costs ( $\Delta C$ ) and quality adjusted life years (QALYs) gained ( $\Delta E$ ), the ICER will be calculated by dividing the incremental cost ( $\Delta C$ ) by the incremental effectiveness ( $\Delta E$ ) in terms of QALYs gained by the RAMP-HT intervention compared to usual care. The ICER will be compared against the threshold value of 1 GDP (Gross Domestic Product) per capita of Hong Kong / QALY (HK\$295,303, 20137) to determine lifetime cost effectiveness of RAMP-HT.

The Markov models will be analysed by the TreeAge Pro Suite (TreeAge Software, Inc, Williamstown, MA) which can run Markov models.

Data sources are summarized in the table below:

Propose	Item/ unit	Data collection methods
Effectiveness	Incidence of CVD, ESRD and all-cause mortality	Anonymous 5-year dataset of diagnosis record (ICPC-2 and ICD-9-CM) to be extracted by HA statistics team from the HA CMS database #
Direct Medical Costs	(i)Cost of RAMP-HT	(i) In-depth costing of RAMP-HT by 

- set-up and operation costs questionnaires to be completed by HA clusters, GOPCs

- central administration cost questionnaire completed by

	
(ii)Public medical costs of RAMP-HT and usual care group; with complications and without complications
 
(iii)Private direct medical costs
	
Finance Office in HA Head Office
 
(ii)Public healthcare service cost will be estimated by the products of :
 
 
- Public healthcare service utilization rates will be extracted from the 5-year HA CMS dataset.
 
- Unit cost of each healthcare service published in the HKSAR Government Gazette
 
 
(iii)Private medical cost questionnaire administered by telephone survey on 230 RAMP-HT and 218 usual care HT subjects

Calculation of quality adjusted life years (QALY)	SF-6D Health preference values of HT patients without and with complications	SF-12v2 HRQOL data from 410 RAMP-HT and 388 usual care HT patients collected in our previous PRO surveys from May 2013 to March 2014 will be converted to SF-6D preference values.
Cohort Life-time Mortality estimates	
(i) HT related mortality
 
(ii) Mortality from other causes
	
(i)Annual HT-related mortality rates will be estimated from the annual incidence of HT complications and published mortality rates of the respective complications.
 
(ii) Hong Kong standard life table will be used as a

		benchmark for the estimation of mortality from other causes adjusted for age and sex)
--	--	---------------------------------------------------------------------------------------

The Markov modelling will run on the following assumptions:

1. Each HT patient will develop only one HT complication in his/her lifetime.
2. HT patients without complications will not die from HT related death, but may die from other cause of death.
3. HT patients with complications may die from either HT-related death or other cause of death.
4. RAMP-HT is effective in reducing HT complications for a period of 5 year; thus the transition probability adjustment of CVD/ESRD development (as determined by the annualized hazard ratio obtained from our long-term effectiveness analysis) will be applied to the model of the RAMP-HT cohort in the first five years. After 5 years, the RAMP-HT will have the same transition probabilities of developing HT complications as usual care HT cohort.
5. RAMP-HT is repeated every 12-24 months and the effectiveness of RAMP-HT will not decrease over time; thus the 5-year effect of RAMP-HT can be annualized. Adjustment will be made on the average duration of repeat RAMP-HT based on available empirical data in order to avoid over-estimation of the RAMP-HT cost.
6. The medical cost (public and private) of HT patients in usual care and RAMP-HT programme is the same for the same HT health status except for the additional RAMP-HT cost.
7. All costs and health preference will be discounted by an annual rate of 3.5% as recommended by the guidance of National Institute for Health and Clinical Excellence (National Institute for Clinical Excellence 2008).

[Word Count: 3968 ]

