#### Exclusion criteria

1. Patients who had a diagnosis of any HT complications defined by relevant ICPC-2 and/or ICD-9-CM diagnosis codes (defined in the "Methods" section) on or before baseline\*
2. Patients diagnosed to have Diabetes Mellitus (DM) on or before 31 March 2017, defined by ICPC-2 codes of T89 or T90
3. Patients exclusively managed by Specialist Out-Patient Clinic (SOPC) on or before baseline\*

To reduce selection bias, the RAMP-HT and usual care subjects will be matched in baseline covariates using the propensity score matching method:

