**HA CMS Data Extraction of Incidence of HT Complications and All-cause Mortality**

Our RAMP-HT QOC study will have collected anonymous 3-year follow up HA CMS data of the cohorts available by November 2015. This study plans to extend the follow up period for an additional 2 years to measure the 5-year incidence of CVD, ESRD and mortality outcomes of these HT patient cohorts from 1 Oct 2011 to 31 March 2017. The data extraction will be carried out by the HA statistics team. Each patient in the cohorts (RAMP-HT and usual care groups) will be observed from baseline to the first occurrence of any of the outcome events until 31 March 2017, with CMS documented diagnoses defined by the relevant ICPC-2 and ICD-9-CM codes below:

1. Cardiovascular disease (CVD) is defined as the presence of any of coronary heart disease (CHD), heart failure or stroke. CHD includes all ischaemic heart disease, myocardial infarction (MI), coronary death or sudden death as indicated by the ICPC-2 K74 to K76 or ICD-9-CM 410.x, 411.x to 414.x, 798.x codes. Heart failure is defined as the ICPC-2 K77 or ICD-9-CM 428.x codes. Stroke (fatal and non-fatal stroke) is defined by the ICPC-2 K89 to K91 or ICD-9-CM 430.x to 438.x codes.
2. End Stage Renal Disease (ESRD) is defined by any of ICD-9-CM 250.3x, 585.x, 586.x, or an estimated Glomerular Filtration Rate (eGFR)  $<15\text{mL/min}/1.73\text{m}^2$ , according to the definition of the National Kidney Foundation.
3. Mortality is defined by a documented death in the Hong Kong Death Registry.

The definitions of each HT complication are determined by the clinician co-investigators and endorsed by clinicians of the HA.

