#### *(ii) Direct Medical Costs of HT patients*

The medical cost analysis will focus on the direct medical costs involved in the care of HT patients without or with specific HT complications (i.e. CHD, heart failure, stroke and ESRD) in both public and private healthcare sectors; indirect cost (e.g. opportunity cost) and non-medical costs (e.g. transportation cost, carer cost) will not be measured.

Public medical costs will be estimated from products of the unit costs (published in the HKSAR Government Gazette and Hospital Authority ordinance (Chapter 113) of charges for non-entitled persons) and the utilization rates of 1) dispensed drugs (*note: self-financed drugs will be considered as private medical cost, see below*), 2) laboratory tests and investigations, 3) healthcare services including general outpatient clinics (GOPC), specialist outpatient clinics (SOPC), allied health services (e.g. dietician, physiotherapist or occupational therapist), accident and emergency (A&E) department and 4) admissions to hospital in the 12 months before baseline and at 12, 24, 36, 48 and 60 months after study enrolment for each patient in the study cohorts. The data extraction will be carried out by the HA statistics team.

Private direct medical costs include the cost of all private Western doctor and Chinese medicine practitioner consultations, private hospitalisation and self-medications inclusive of self-financed medications prescribed by the HA. 598 HT patients (307 RAMP-HT patients and 291 usual care patients) who were recruited from HA GOPCs for the longitudinal evaluation of patient reported outcomes (PRO) in the evaluation of QOC RAMP-HT study from May 2013 to March 2014 will be invited to complete a “private medical cost of HT questionnaire” (Appendix E) by telephone. The questionnaire is adapted from the costing questionnaire that was used in our in-depth study on the cost-effectiveness analysis of RAMP-DM that had proven feasibility and validity (HHSRF # EPC\_HKU-1A).

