### **Cost Analysis of RAMP-HT**

Descriptive statistics will be used to summarize the costs of RAMP-HT and annual direct medical costs for RAMP-HT and usual care patients at baseline and over each of 5 subsequent years, overall, and by the presence of complications. The cost of each healthcare service will be derived by multiplication of the unit cost from Gazette and Hospital Authority ordinance and the number of respective services used by the patients. To avoid double counting the cost of drugs and laboratory tests, the Government Gazette cost of each GOPC and SOPC attendance will be adjusted by a factor of 0.7 to include only the manpower cost. The total public medical costs will be calculated by summing up all costs of drugs, laboratory tests and each healthcare service utilisation. The private medical costs will be estimated by summarizing the self-reported costs of private consultations, self-medication and private hospitalisation. The average annual public and private direct medical costs per patient will be analysed by HT complication status (CHD, heart failure, stroke and ESRD), and by RAMP-HT and usual care HT groups. To determine whether the direct medical costs of the RAMP-HT cohort is higher than the usual care HT cohort, one sided independent t-test will be performed.

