Costs	Cost of RAMP-HT Direct medical costs for each health status (i.e. Hypertension without complications, HT with Coronary Heart Disease, HT with Stroke, HT with Heart failure or HT with End Stage Renal Disease)
Health utility	Health utility for each health status (i.e. Hypertension without complications, HT with Coronary Heart Disease, HT with Stroke, HT with Heart failure or HT with End Stage Renal Disease)

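### One average annual public cost per complication, estimated on short follow-up after new events, is charged in every year of a lifetime model; if the event year costs more than later years, the ICER is moved in favour of RAMP-HT

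*Combined protocol and SAP*

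**What the plan says.** Under Cost Effectiveness Analysis of RAMP-HT by Markov Modeling, the inputs to the lifetime model are "The average cost and preference values for each HT disease state (with or without specific complication". The cycle is one year. A patient who survives a complication remains in that complication's state; the text names no separate post-acute state.

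The cost inputs come from Cost Analysis of RAMP-HT: "The average annual public and private direct medical costs per patient will be analysed by HT complication status (CHD, heart failure, stroke and ESRD". The descriptive summary there runs "over each of 5 subsequent years, overall, and by the presence of complications", that is, by study year and not by time since the event. Table 1 lists "Direct medical costs for each health status (i.e. Hypertension without complications, HT with Coronary Heart Disease" and the other three complications, with one value for each.

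Public utilisation is collected for the year before baseline and "at 12, 24, 36, 48 and 60 months after study enrolment for each patient in the study cohorts". Follow-up covers "mortality outcomes of these HT patient cohorts from 1 Oct 2011 to 31 March 2017". The first exclusion criterion removes "Patients who had a diagnosis of any HT complications defined by relevant ICPC-2" and/or ICD-9-CM codes on or before baseline, so every complication that is costed in the cohorts is a new one.

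The model assumptions set state costs equal in the two arms apart from the programme cost, limit the effect on complications to five years, and discount at 3.5% a year. The ICER is primary outcome 3 and decides hypothesis 4. No sensitivity analysis of the state costs is described.

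**The concern.** The average is formed over one mix of person-time and applied to another. In the cohort, the time after a complication is short, so the first year after the event has a large weight. In the model a survivor may stay in the state for many years, and the first year is a small part of that stay. A single average carries the event-year weight from the short window into every later cycle.

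If the event year is dearer than later years, for example because of an acute admission, each complication is charged too much over a lifetime. State costs are equal by arm, so medical savings in the model come from avoided complications. Overstating their cost overstates the savings, lowers incremental cost and lowers the ICER that is compared with HK$295,303 per QALY.

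**Working it through.** The plan states no complication cost, no ratio of event-year to later-year cost and no ICER, so there is no figure of its own to reproduce. The check has four steps.

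**1. Weight of the event year in the data.** Inputs: new events only (exclusion criterion 1) and a window of about 5 years (data extraction section). Assume events spread evenly over 5 years and no deaths.
- Mean time observed in the first 12 months after the event: (4 × 1 + 1 × 0.5) / 5 = 0.9 years.
- Mean time observed after the event: 5 / 2 = 2.5 years.
- Share: 0.9 / 2.5 = 36%.

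Counting whole study years gives 5 / (5 + 4 + 3 + 2 + 1) = 33%. With a constant hazard from the plan's 8% five-year CVD incidence in usual care, −ln(0.92)/5 = 0.0167 a year, the share is 36% without deaths, and 38%, 40% and 44% with assumed post-event mortality of 5%, 10% and 20% a year.

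**2. Weight of the event year in the model.** For an assumed stay of 5, 10 or 15 years it is 1/5 = 20%, 1/10 = 10% or 1/15 = 7%. The mismatch between steps 1 and 2 needs no cost assumption.

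**3. Effect on lifetime cost per case.** Let k be event-year cost divided by later-year cost (assumed), and set later-year cost to 1. The single average is 0.36k + 0.64. With discount factors 1.035^−t for t = 0 to T − 1 and sum S (4.673, 8.608 and 11.921 for T = 5, 10 and 15):

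ratio = (0.36k + 0.64) × S / (k + S − 1)

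Example, k = 3 and T = 10: 1.72 × 8.608 / (3 + 7.608) = 14.81 / 10.61 = 1.40.

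| k | Single average | T = 5 | T = 10 | T = 15 |
|---|---|---|---|---|
| 0.8 | 0.93 | 0.97 | 0.95 | 0.94 |
| 1 | 1.00 | 1.00 | 1.00 | 1.00 |
| 2 | 1.36 | 1.12 | 1.22 | 1.25 |
| 3 | 1.72 | 1.20 | 1.40 | 1.47 |
| 4 | 2.08 | 1.27 | 1.54 | 1.66 |
| 5 | 2.44 | 1.31 | 1.67 | 1.83 |

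A yearly cohort model gives a similar picture for avoided complication cost. It used a hazard ratio of ln(0.93)/ln(0.92) = 0.870 for five years (from the plan's 7% and 8%), equal hazards afterwards and 3.5% discounting. It also assumed excess post-event mortality of 3% or 8% a year, background mortality of 0.8% rising 9% a year, and a complication hazard rising 5% a year. The ratio of single-average to two-phase cost was 0.94 at k = 0.8, 1.00 at k = 1, 1.25-1.27 at k = 2, 1.45-1.51 at k = 3 and 1.75-1.89 at k = 5.

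**4. Pre-event years.** The plan does not say whether the years before an event, in a patient who later has one, enter that complication's average. If they do, and cost an assumed 0.3-0.5 of a later year, the lifetime ratio per case (post-event mortality 5-20% a year) becomes 0.65-0.86 at k = 2, 0.69-0.96 at k = 3 and 0.74-1.12 at k = 5. Over most of that range, complication cost is understated.

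**The case against.** A reader might infer that the window is dominated by the event year, that every complication cost is therefore overstated, and that the ICER is certainly biased towards RAMP-HT. The documents do not support that.

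- **Dominance.** The event year is a minority of observed post-event time. It makes up more than half of observed post-event cost only if k exceeds (1 − share) / share, which is about 1.8 without deaths and 1.3 at 20% annual mortality. No value of k is given.
- **All four complications.** The outcome definitions count all ischaemic heart disease, heart failure codes, and ESRD by code or by eGFR below 15. These can be met by a chronic diagnosis or a laboratory value, without an acute admission. For ESRD nothing in the plan suggests that cost falls after the first year.
- **Length of stay.** The 10 and 15 years are assumptions. Patients may be up to 79 at entry and complications carry excess mortality, so the 5-year column may be nearer for some states.
- **Other features.** The model allows one complication per lifetime, and the plan does not say whether acute cost is charged to patients who die at once. Either could understate complication cost, so the net effect on the ICER is not shown.
- **Private costs.** These come from a telephone survey of a subsample, so the window argument covers public costs only.
- **Figure 1.** It is not available in the text reviewed. A post-acute state there cannot be fully excluded, although the Markov section and Table 1 describe none.

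All of these stand as limits on direction and size. None removes the mismatch in steps 1 and 2 of the working, and the silence on pre-event years is a further reason to define the state costs.

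**Conclusion.** The point holds in a conditional form. A single average public cost per complication, estimated on new cases with at most about 5 years of post-event follow-up, gives the event year about 36% of the weight (36-44% with deaths) where a 10- to 15-year modelled stay would give it 7-10%. If event-year cost exceeds later-year cost, and the average is taken over post-event time only, lifetime complication cost is overstated and the ICER is moved in favour of RAMP-HT. For assumed ratios of 2 to 5 the overstatement of lifetime complication cost is 12-31% over a 5-year stay, 22-67% over 10 years and 25-83% over 15 years.

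These percentages refer to complication cost, not to the ICER. The shift in the ICER cannot be computed, because the plan gives no programme cost, state costs or preference values, and it is not shown that the comparison with the threshold would change. The bias is nil at a ratio of 1 and reverses below 1, the ratio may differ by complication, and pooling pre-event years can also reverse the direction.

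**What to change.** In Cost Analysis of RAMP-HT, the Markov section and Table 1:

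1. Replace the single public cost of each complication by two: cost in the 12 months from the event, and mean annual cost in later years. Estimate both from the public utilisation and diagnosis data already being extracted.
2. Apply the first in the cycle of entry to the state and the second in every later cycle.
3. State that time before the event belongs to the no-complication state.
4. Report the single-average version as a sensitivity analysis. If the ratio proves close to 1, the two versions will agree.

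The cost is four extra model parameters and one further split of the cost table, with no new patients. Event dates must be linked to utilisation dates, because utilisation is now indexed from enrolment. Later-year costs will rest on fewer person-years and will be less precise for the rarer states, such as ESRD and heart failure.

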### **c Aim, objectives and Hypotheses:**

Aim and objectives:

The aim of this study is to evaluate the cost-effectiveness of the RAMP-HT of the HA in primary care patients with uncontrolled hypertension.

The objectives are to

1. Evaluate the long term (5-year) effectiveness of RAMP-HT compared to usual care in reducing cardiovascular complications, end-stage renal disease and all-cause mortalities in a cohort of primary care patients with uncontrolled hypertension at baseline
2. Estimate the direct medical cost of RAMP-HT and other health services

among primary care HT patients with or without complications

3. Evaluate the cost-effectiveness of RAMP-HT, compared to usual care, in gaining one Quality-Adjusted Life Year (QALY) in primary care patients with uncontrolled hypertension

Hypotheses:

1. RAMP-HT is more effective in reducing 5-year cardiovascular complications, end stage renal disease and all-cause mortality among primary care patients with uncontrolled hypertension compared to usual care
2. The direct medical cost of RAMP-HT patients, for the same disease complication status, is not higher than that of usual care except for the RAMP-HT cost
3. The direct medical cost of HT patients with one or more complications is higher than that of HT patients without any complication
4. RAMP-HT is cost-effective compared to usual care, i.e. the incremental cost-effectiveness ratio (ICER) per QALY gained is below the threshold value of 1 annual GDP (Gross Domestic Product) per capita of Hong Kong (HK\$295,303, 2013), which is the benchmark recommended by the World Health Organization

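### Markov state costs and SF-6D values are unadjusted averages by complication status, so the cost and utility loss per complication may be overstated and the ICER may be biased towards RAMP-HT

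*Combined protocol and SAP*

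**What the plan says.** Three parts of the data processing and analysis section, and Table 1, define the inputs.

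- **Costs.** Cost Analysis of RAMP-HT begins: "Descriptive statistics will be used to summarize the costs of RAMP-HT and annual direct medical costs". For the states it adds: "The average annual public and private direct medical costs per patient will be analysed by HT complication status". The only test named there is a one-sided t-test between arms.
- **Utilities.** Health Preference by HT Complication Status says: "Independent t-test will be used to compare the SF-6D values of HT patients with each complication to those without any complication".
- **Model.** The Markov section takes these results forward: "The average cost and preference values for each HT disease state (with or without specific complication) obtained from the cost and" preference studies. Table 1 lists "Direct medical costs for each health status" and "Health utility for each health status". Neither parameter is indexed by age, sex or comorbidity.

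Model assumption 6 gives both arms the same medical cost in the same health state, apart from the programme cost. Model assumption 4 lets RAMP-HT act by lowering transitions into complication states in the first five years. Hypothesis 3 reads: "The direct medical cost of HT patients with one or more complications is higher than that of HT patients without any complication".

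**The concern.** The model moves a patient from the complication-free state to a complication state and applies the whole difference between the two averages as the consequence of the event. The two groups of patients are not exchangeable. The cohort spans ages 18 to 79, and the programme itself stratifies patients by 10-year CVD risk calculated from their risk factors. Those who reach a complication state are likely to be older and less healthy, and would probably have had higher costs and lower SF-6D scores without the event.

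If the crude gap exceeds the causal gap, each avoided complication is credited with too large a saving and too many QALYs. Incremental cost falls, incremental QALYs rise, and the ICER falls. It is then compared with HK$295,303 per QALY.

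The bias lies in the contrast between states, not between arms, so the plan's safeguards do not reach it. Propensity matching balances RAMP-HT against usual care. Covariate adjustment is confined to the Cox models, and age and sex adjustment to other-cause mortality. No regression, standardisation, before-after contrast or sensitivity analysis is planned for the state inputs.

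**Working it through.** The plan states no figure for this point, so there is none to reproduce. The check asks how far the ICER moves if part of the crude contrast is background.

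**Inputs from the documents.** 5-year CVD incidence 7% (RAMP-HT) and 8% (usual care), from the sample size section; effect in years 1-5 only, equal transitions afterwards; 3.5% discounting; threshold HK$295,303.

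**Assumed inputs.** Background mortality m = 0.6% in the first year, rising by a factor of 1.10 a year; extra mortality with a complication 4% a year; complication-free state HK$10,000 a year and utility 0.80 at the start; programme HK$1,500 a year for five years while complication-free; 40 annual cycles; one pooled complication state.

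**Model.** Annual event probability is 1 − (1 − 0.08)^(1/5) = 0.01654 for usual care and 1 − (1 − 0.07)^(1/5) = 0.01441 for RAMP-HT in years 1-5. With f complication-free and c with a complication, each year f becomes f(1 − m)(1 − p), and c becomes [f·p + c](1 − m)(1 − 0.04). ICER = ΔC/ΔQ.

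**Age gap.** Let the causal contrast be HK$30,000 a year and 0.08 utility. Let background cost rise by s_c and utility fall by s_u per year of age. If cases are g years older, the crude contrast is 30,000 + g·s_c and 0.08 + g·s_u. For g = 6, s_c = 300 and s_u = 0.002 it is 30,000 + 1,800 = HK$31,800 and 0.08 + 0.012 = 0.092.

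| g (years) | s_c, s_u | ICER, causal contrast | ICER, crude contrast | Change |
|---|---|---|---|---|
| 3 | 300, 0.002 | 130,432 | 127,059 | −2.6% |
| 3 | 600, 0.004 | 141,473 | 134,278 | −5.1% |
| 6 | 300, 0.002 | 130,432 | 123,765 | −5.1% |
| 6 | 600, 0.004 | 141,473 | 127,430 | −9.9% |
| 10 | 300, 0.002 | 130,432 | 119,495 | −8.4% |
| 10 | 600, 0.004 | 141,473 | 118,796 | −16.0% |

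**Which gap is plausible.** If the hazard rises log-linearly with age at rate β and age is normal, cases are older on average by β × SD². With β of 0.05 to 0.07 and an SD of 10 (both assumed), that is 5 to 7 years. The age limit below 80 shortens this: with an assumed parent mean of 65 and parent SD of 10, the gap is 3.5 to 4.7 years. The rows for 3 and 6 years bracket that range, with the ICER 2.6-9.9% too low.

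**Age and comorbidity together.** Take instead a crude contrast of HK$30,000 and 0.10 with flat state values. Then ΔC = 4,808, ΔQ = 0.0416 and the ICER is 115,674. If a share of both contrasts is background, the adjusted ICER is:

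- 10%: 123,645 (+6.9%)
- 20%: 131,927 (+14.1%)
- 30%: 140,540 (+21.5%)
- 40%: 149,504 (+29.2%)

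The highest ICER in any run is 149,504, about half the threshold (149,504 / 295,303 = 0.51). These runs assume that the crude gap exceeds the causal gap, so their common direction is a consequence of that assumption, not evidence for it.

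**The case against.** The strongest objection is that direction and size are not shown. The documents give no age, cost or utility by complication status. SF-12 and private-cost data come from patients recruited in general out-patient clinics, and the private-cost survey expects 25% attrition. Patients with severe stroke or ESRD may be missing, which would shrink the crude gap. The cohort also excludes prior complications, diabetes and patients managed only by specialists, and is capped below age 80, which narrows differences in background health. This stands: the most that can be said is that the crude gap may overstate the causal one. It does not remove the problem, because the exclusions leave a wide age range and no step in the plan would show whether the forces cancel.

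A reader might infer that the cost-effectiveness conclusion is at risk. The illustrations do not support that, since none crosses the threshold. Because they rest on assumed inputs, they do not prove the opposite either.

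A reader might also infer that Hypothesis 3 is invalid because of confounding. As worded it states that one group costs more than another and attributes nothing to the complication. A crude comparison answers it.

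Finally, full regression may not be workable for the survey data. The private-cost sample is 230 + 218 = 448 patients. The SF-12 sample is 307 + 291 = 598 in the sample size section and 410 + 388 = 798 in the data source table. These are spread over five health states. The documents do not say that the surveys can be linked to the anonymous clinical extract. This stands and limits the fix. The t-test on SF-6D is peripheral, since the means, not the test, enter the model.

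**Conclusion.** The point holds as a gap in the plan. A primary outcome rests on a non-randomised contrast between health states, with no planned adjustment and no planned check. The ICER may be biased in favour of RAMP-HT, provided that RAMP-HT lowers complications as model assumption 4 has it and that age and background health outweigh survivor or responder selection in the surveys.

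The size is illustrative only: roughly 3-16% of the ICER for an age gap of 3 to 10 years acting through the state contrast, probably towards the lower part of that range given the age cap, and more if comorbidity also contributes. No illustration reaches HK$295,303. The plan should be changed before the final model is built, but nothing here shows that the study's conclusion would be reversed.

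**What to change.** - **Public costs.** Estimate state costs by regression, for example a GLM with log link, on complication state with age, sex, smoking, baseline comorbidity and the patient's own cost in the 12 months before baseline. Enter covariate-standardised values by state and age. The covariates are already matching variables, and public costs are already to be extracted for the pre-baseline year and yearly to 60 months. Prior complications are an exclusion, so the pre-baseline year is complication-free for the whole cohort. Comparing that year's cost between later cases and non-cases would show directly whether background differences exist.
- **SF-6D and private costs.** Adjust at least for age and sex. Add other covariates only where numbers per state and data linkage allow.
- **Sensitivity analysis.** Report the ICER with the crude averages beside the adjusted one.
- **Hypothesis 3.** Keep it as a descriptive comparison. Use the adjusted estimate if the difference is attributed to the complication.

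For public costs this needs no new data, only more analysis and age-indexed model inputs. The ICER may become less favourable to RAMP-HT.
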